9.3.2 Other Secondary Endpoints

The following secondary endpoints will be analyzed for the ITT analysis set.

- The proportion of subjects with endoscopic improvement, defined as an Endoscopic Response Score of 0 or 1, with at least a 1 point reduction from baseline in the endoscopic score at week 8
- The proportion of subjects in clinical remission at Weeks 2, 4, and 8, defined as a score of 0 for rectal bleeding and “0” or “1 with at least 1 point reduction from baseline” for stool frequency in the Clinical Response Score subset
- Time to normal stool pattern, defined as time in days from randomization to the first day of 3 consecutive days with a stool frequency score of 0, based on subject daily diary
- The change from baseline in rectal bleeding score at Weeks 2, 4, and 8, based on subject daily diary
- The change from baseline in serum CRP levels at Weeks 2, 4, and 8
- The change from baseline in fecal calprotectin levels at Week 8

The proportion of subjects with endoscopic improvement will be analyzed using the same statistical method used for the primary efficacy analysis.

The proportion of subjects in clinical remission at Weeks 2, 4, and 8 will be analyzed by the generalized estimating equations (GEE) approach as longitudinal binary outcomes. The model will include treatment, time, and treatment- by-time interaction. The clinical remission rates and odds ratio will be estimated for each time point. The overall treatment difference over 8 weeks will be estimated as the main effect for treatment in the model. The missing values will be imputed as non-remission, and an unstructured working correlation matrix will be used.

The time to normal stool patten will be analyzed using the same statistical method used for the analysis of the time to cessation of rectal bleeding.

The change from baseline in rectal bleeding score and serum CRP levels at Weeks 2, 4, and 8 will be analyzed by repeated-measures analysis of covariance (ANCOVA) models that include treatment, time, and treatment-by-time interaction as fixed effects, and the corresponding baseline value as a covariate. The adjusted changes from baseline and their difference between treatment groups will be estimated for each time point. The overall treatment difference over 8 weeks will be estimated as the main effect for treatment in the model. The missing values will be left as missing, and an unstructured correlation matrix will be assumed.

The change from baseline in fecal calprotectin levels at Week 8 will be analyzed by an ANCOVA model that includes treatment as a factor and the baseline value as a covariate. The adjusted changes from baseline and their difference between treatment groups will be estimated.

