#### Secondary Endpoints

1. The proportion of subjects with endoscopic improvement, defined as an Endoscopic Response Score of 0 or 1, with at least a 1 point reduction from baseline in the endoscopic score at Week 8

2. The proportion of subjects in clinical remission at Weeks 2, 4, and 8, defined as a score of 0 for rectal bleeding and 0 or 1 with at least 1 point decrease from baseline for stool frequency in the Clinical Response Score subset
3. Time to normal stool pattern, defined as time in days from randomization to the first day of 3 consecutive days with a stool frequency score of 0, based on subject daily diary
4. The change from baseline in rectal bleeding score at Weeks 2, 4, and 8, based on subject daily diary
5. The change from baseline in serum CRP levels at Weeks 2, 4, and 8
6. The change from baseline in fecal calprotectin levels at Week 8
7. The change from baseline to each scheduled assessment for published and validated domain scores of the IBDQ
8. Safety, assessed by incidence and severity of AEs and abnormal laboratory values

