## **9.6 Endpoint Assessments**

### **9.6.1 General Considerations**

All statistical tests will be conducted at a two-sided 0.05 significance level.

Quantitative variables will be described with the number of non-missing values, mean, standard deviation, median, and minimum/maximum values. Qualitative variables will be described with the number and percentage of subjects with each qualitative characteristic. Missing values will not be included in the calculation of percentages.

All data will be listed by individual subject and trial visit.

The efficacy data captured during the 8-week open-label mesalamine 4g/day treatment will be descriptively summarized and used for exploratory purposes only.

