### **9.6.3 Secondary Endpoints**

Key secondary endpoints are the following:

1. The proportion of subjects with remission in the primary endpoint and the PGA score of  $\leq 1$  (Modified Mayo) at Week 8
2. Time to cessation of rectal bleeding, defined as time in days from randomization to the first day of 3 consecutive days with a rectal bleeding score of 0, based on subject daily diary

Secondary endpoints are the following:

1. The proportion of subjects with endoscopic improvement, defined as an Endoscopic Response Score of 0 or 1, with at least a 1 point reduction from baseline in the endoscopic score at Week 8
2. The proportion of subjects in clinical remission at Weeks 2, 4, and 8, defined as a score of 0 for rectal bleeding and 0 or 1 with at least 1 point decrease from baseline for stool frequency in the Clinical Response Score subset
3. Time to normal stool pattern, defined as time in days from randomization to the first day of 3 consecutive days with a stool frequency score of 0, based on subject daily diary
4. The change from baseline in rectal bleeding score at Weeks 2, 4, and 8, based on subject daily diary
5. The change from baseline in serum CRP levels at Weeks 2, 4, and 8
6. The change from baseline in fecal calprotectin level at Week 8
7. The change from baseline to each scheduled assessment for published and validated domain scores of the IBDQ
8. Safety, assessed by incidence and severity of AEs and abnormal laboratory values

The key secondary endpoints will be analyzed by a fixed-sequence procedure according to the pre-specified order to maintain the overall Type 1 error rate to a two-sided 5%.

If the primary efficacy analysis demonstrates a statistically significant difference between the treatment groups, the first key secondary endpoint will be compared using the same statistical method used for the primary efficacy analysis at a two-sided 0.05 significance level. If the analysis for the first key secondary endpoint is statistically significant, the second key secondary endpoint will be compared by the log-rank test at a two-sided 0.05 significance level.

Other secondary endpoints will be analyzed individually at a two-sided 0.05 significance level.

The proportion of subjects with endoscopic improvement will be analyzed using the same statistical method used for the primary efficacy analysis.

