The proportion of subjects in clinical remission at Weeks 2, 4, and 8 will be analyzed by the generalized estimating equations approach as longitudinal binary outcomes. The model will include treatment, time, and treatment- by-time interaction. The clinical remission rates and odds ratios will be estimated for each time point.

The time to normal stool pattern will be analyzed using the same statistical method used for the analysis of the time to cessation of rectal bleeding.

The change from baseline in rectal bleeding score and serum CRP levels at Weeks 2, 4 and 8 will be analyzed by repeated-measures analysis of covariance (ANCOVA) models that include treatment, time, and treatment-by-time interaction as fixed effects, and the corresponding baseline value as a covariate based on the observed data. The adjusted changes from baseline and their difference between treatment groups will be estimated for each time point. The change from baseline in the fecal calprotectin level at Week 8 will be analyzed by an ANCOVA model that includes treatment as a factor and baseline value as a covariate.

The efficacy data captured during the 8-week open-label mesalamine 4 g/day treatment period, will be used for exploratory purposes only.

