2.2.3 Secondary endpoints

- The proportion of subjects with endoscopic improvement, defined as an Endoscopic Response Score of 0 or 1, with at least a 1 point reduction from baseline in the endoscopic score at Week 8
- The proportion of subjects in clinical remission at Weeks 2, 4, and 8, defined as a score of 0 for rectal bleeding and "0" or "1 with at least 1 point decrease from baseline" for stool frequency in the Clinical Response Score subset
- Time to normal stool pattern, defined as time in days from randomization to the first day of 3 consecutive days with a stool frequency score of 0, based on subject daily diary
- The change from baseline in rectal bleeding score at Weeks 2, 4, and 8, based on subject daily diary

- The change from baseline in serum CRP levels at Weeks 2, 4, and 8
- The change from baseline in fecal calprotectin levels at Week 8
- The change from baseline to each scheduled assessment for published and validated domain scores of the IBDQ
- Safety assessed by incidence and severity of AEs and abnormal laboratory values

3 Trial design

This is a randomized, double-blind, placebo-controlled, parallel-group, multicenter, international, phase 3 trial to investigate the safety and efficacy of mesalamine 4 g extended release granules (sachet) for the induction of clinical and endoscopic remission in subjects with active, mild to moderate active UC. Following completion of Visit 0/screening, the subjects will be randomized to a treatment group during Visit 1/baseline. Each subject will receive a total of 8 weeks of double-blind treatment with either:

- one mesalamine 4 g extended release granules (sachet) QD (4 g/day) OR
- one 4 g placebo sachet to match mesalamine extended release granules (sachet)

Dose will be administered QD at least 1 hour before or at least 2 hours after a meal at approximately the same time each day. The sachet will be emptied on the tongue and swallowed with at least 8 ounces (240 mL) of water. Following randomization, the first dose of investigational medicinal product (IMP) will be administered at the site during Visit 1.

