9.4.2 Efficacy Endpoints During 8-week Open-label Trial Period

The following endpoints will be descriptively summarized by the treatment received during the double-blind period for subjects who receive the 8-week open-label treatment.

- The proportion of subjects in remission, defined as rectal bleeding score of 0 and stool frequency score of “0” or “1 with at least 1 point decrease from baseline” with an endoscopic score of 0 or 1 in the Clinical and Endoscopic Response Score at Week 16
- The proportion of subjects with endoscopic improvement, defined as an endoscopic score of 0 or 1, with at least a 1 point reduction from baseline in the endoscopic score at Week 16
- The proportion of subjects in clinical remission, defined as a score of 0 for rectal bleeding and “0” or “1 with at least 1 point decrease from baseline” for stool frequency in the Clinical Response Score subset at Weeks 10 and 16
- The change from baseline in serum CRP levels at Weeks 10 and 16
- The change from baseline in fecal calprotectin levels at Weeks 16
- The change from baseline in the IBDQ domain and total scores at Weeks 10 and 16

10 Safety

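### Is it a flaw that CRP and fecal calprotectin are compared between arms on the raw scale only?

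*SAP*

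**What the plan says.** Both markers are non-key secondary endpoints, defined as differences from baseline: "The change from baseline in serum CRP levels at Weeks 2, 4, and 8" (Protocol 2.2) and "The change from baseline in fecal calprotectin levels at Week 8" (SAP 2.2.3).

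The analyses follow those definitions. For CRP, SAP 9.3.2 says "The change from baseline in rectal bleeding score and serum CRP levels at Weeks 2, 4, and 8 will be analyzed by repeated-measures analysis"; its terms are treatment, time, their interaction and the baseline value. Calprotectin has a single post-baseline time point and gets an ordinary ANCOVA: "The change from baseline in fecal calprotectin levels at Week 8 will be analyzed by an ANCOVA model that includes treatment as a factor". Baseline is again the covariate. Protocol 9.6.3 plans the same: "The change from baseline in the fecal calprotectin level at Week 8 will be analyzed by an ANCOVA model". In each case the reported estimate is the adjusted change and its difference between arms. Neither document uses the word untransformed, but a model for change in levels with no transformation named reads as raw scale.

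SAP 9.1 tests the secondary endpoints outside the fixed sequence at a two-sided 0.05 without multiplicity adjustment. SAP section 12 declares no departure from the protocol's analyses.

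**The concern.** CRP and calprotectin are concentrations that cannot fall below zero, and a few very high values can dominate a mean and its standard error. If a drug lowers every value by the same proportion, a log analysis uses the data better, and a raw analysis may miss a real effect. A statistician would therefore look for a log-scale model or a geometric mean ratio, and there is none. The sensitivity analyses in SAP 9.2.2 concern the primary endpoint. The percentage changes in SAP 10.3.1 are descriptive and belong to the safety laboratory groups, which do not list these markers. The general descriptive rule in Protocol 9.6.1 ("Quantitative variables will be described with the number of non-missing values, mean, standard deviation, median, and minimum/maximum values") would reveal skew but tests nothing between arms.

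Two things would be at stake: the verdict on two markers named in the secondary objectives could rest on an unsuitable scale, and a log analysis added after unblinding could be a way to pick the favourable answer.

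**Working it through.** **1. Inputs.** From the documents: 110 randomized per group (SAP 3.2), two-sided 0.05 (SAP 9.1), and ANCOVA of change on treatment and baseline (SAP 9.3.2). Not in the documents, hence assumed: log-normal values, a log-SD between 0.5 and 1.5, a correlation of 0.4 between log baseline and log Week 8, complete data, and the form of the drug effect.

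**2. The plan's own figure.** There is none for these markers. The only power claim is for remission, 36% against 18%. With pooled rate 0.27:
- standard error under no effect: √(2 × 0.27 × 0.73 / 110) = 0.0599
- standard error under the assumed effect: √((0.36 × 0.64 + 0.18 × 0.82) / 110) = 0.0586
- z = (0.18 − 1.96 × 0.0599) / 0.0586 = 1.07, so power is 85.7%

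This agrees with the stated minimum of 85% but says nothing about CRP or calprotectin.

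**3. Is the planned test valid?** The calprotectin ANCOVA was simulated with no drug effect: 100 per arm, log-SD 0.7 to 1.5, correlations 0.4 and 0.6. It rejects in 3.9% to 4.9% of trials on the raw scale and in 4.8% to 5.2% on the log scale. Skew of this size does not inflate the raw test.

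**4. Which scale is better?** Each trial was analysed twice: raw change on raw baseline, and log change on log baseline. Power, raw vs log, 110 per arm, 5,000 trials per cell:

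| Drug effect at Week 8 | log-SD 0.5 | 0.8 | 1.0 | 1.5 |
|---|---|---|---|---|
| All values × 0.7 | about 100% for both | 84% vs 94% | 59% vs 82% | 21% vs 49% |
| Only the top 20% of values, × 0.4 | 99% vs 91% | 92% vs 54% | 83% vs 37% | 49% vs 18% |
| Only the lower half of values, halved | 56% vs 99% | 14% vs 82% | 8% vs 67% | 4% vs 39% |

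The log scale wins in rows 1 and 3, apart from the tie at log-SD 0.5 in row 1. The raw scale wins throughout row 2. At log-SD 1.0, row 1 is significant on log only in 25% of trials and on raw only in 2%; row 2 is raw only in 47% and log only in 1%.

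The CRP repeated-measures model behaves alike. It was simulated with 100 per arm, 2,000 trials per scenario, log-SD 1.0, and the Week 8 comparison. With uniform reductions of 20%, 30% and 40% at Weeks 2, 4 and 8, power is 83% raw vs 98% log. If only values above the 75th percentile fall, it is 59% vs 18%.

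The ranking therefore turns on the form of the effect, on which the documents are silent.

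**5. How large is the selection risk?** Two tests at 5% give a chance of at least one false positive between 5% (always agreeing) and 1 − 0.95² = 9.75% (independent). In simulation, claiming whichever scale is significant gives 7.0% to 7.9% for the calprotectin ANCOVA and 7.2% to 8.2% for the CRP model. Those figures describe a practice that needs two candidate analyses. SAP 9.3.2 names one per marker.

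**6. Would a log sensitivity analysis change a result?** Suppose it were added with raw kept as the main scale. If both are significant, or neither is, the verdict is the raw one. If they disagree, the verdict is still the raw one, because the log result would not replace it. The planned conclusion is the same in every case.

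**The case for a change.** The strongest case for acting is timing and cost. CRP and calprotectin appear in the secondary objectives (Protocol 2.1, SAP 2.1.2), and each is tested at 0.05 on a single scale. Under the assumptions above with 100 per arm, the two scales can reach different verdicts in as many as 43% of trials. A log model written down before unblinding would be credible, would need only a few sentences and two outputs, and would spare the sponsor an argument later. The primary endpoint, by comparison, has a long list of robustness checks.

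Much of the factual part stands. No second scale is planned, scale can matter, and a log analysis produced after the results would carry little weight. But such an analysis would be absent from the SAP, so any reader could identify it as post hoc. A geometric mean ratio also estimates something other than a difference in mean concentration. It would supplement the planned comparison and not test its robustness, and no rule is at hand for reading a disagreement. Nor are these two markers treated unlike their peers: the other non-key secondary endpoints in SAP 9.3.2 and 9.4.1 have no sensitivity analysis either.

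Neither document states how values below the assay limit are handled. A rule may sit in the laboratory manual mentioned in Protocol 7.4 or in the separate output shells of SAP section 14, neither of which was available. That is an absent detail with no demonstrated effect on the comparison.

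**Conclusion.** The concern does not hold. Protocol and SAP agree on endpoint, model, covariate and estimate for both markers. The raw-scale test keeps its error rate in simulation, and one analysis per marker is fixed in advance. No better scale has been shown: at log-SD 1.0 the raw analysis loses 23 percentage points of power under a uniform 30% reduction (82 − 59) and gains 46 when only the top fifth of values fall (83 − 37).

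All these sizes rest on assumed log-normal data, an assumed spread, a correlation of 0.4 and complete follow-up. The calprotectin figures were confirmed by repeat simulation; the CRP figures come from a single simulation. The conclusion does not depend on the exact values. It needs only that the planned test is valid and that the ranking of the scales can go either way. The primary and key secondary conclusions are unaffected whatever these markers show. A sponsor may still choose to report geometric mean ratios as supplementary information, but the plan is sound without them.

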9.4 Other Endpoint(s)

9.4.1 Health Related Quality of Life

The change from baseline in the IBDQ will be analyzed for the ITT analysis set.

The following domain scores for the IBDQ (Guyatt et al., 1989)(11) will be calculated by adding up scores from questions included in the domain for each subject at each time point:

- Bowel symptoms: Questions 1, 5, 9, 13, 17, 20, 22, 24, 26, 29
- Emotion function: Questions 3, 7, 11, 15, 19, 21, 23, 25, 27, 30, 31, 32
- Systemic symptoms: Questions 2, 6, 10, 14, 18
- Social function: Questions 4, 8, 12, 16, 28

The total score will be calculated by adding up all scores for each subject at each time point.

The handling of missing score in the calculation of the domain and total scores will be based on McMaster University (2010)(12). If there is only one missing response within a domain, the missing response will be imputed as an average of other responses within the domain. If there are two or more missing responses within a domain, the domain score will be considered missing. For the total score, if there are up to four missing responses, the missing responses will be imputed as an average of other responses. If there are more than four missing responses, the total score will be considered missing.

The change from baseline in the IBDQ domain and total scores at Weeks 2, 4, and 8 will be analyzed by repeated-measures ANCOVA models that include treatment, time, and treatment-by-time interaction as fixed effects, and the corresponding baseline value as a covariate. The adjusted changes from baseline and their difference between treatment groups will be estimated for each time point. The missing values will be left as missing, and an unstructured correlation matrix will be assumed.

9.4.2 Efficacy Endpoints During 8-week Open-label Trial Period

The following endpoints will be descriptively summarized by the treatment received during the double-blind period for subjects who receive the 8-week open-label treatment.

- The proportion of subjects in remission, defined as rectal bleeding score of 0 and stool frequency score of “0” or “1 with at least 1 point decrease from baseline” with an endoscopic score of 0 or 1 in the Clinical and Endoscopic Response Score at Week 16
- The proportion of subjects with endoscopic improvement, defined as an endoscopic score of 0 or 1, with at least a 1 point reduction from baseline in the endoscopic score at Week 16
- The proportion of subjects in clinical remission, defined as a score of 0 for rectal bleeding and “0” or “1 with at least 1 point decrease from baseline” for stool frequency in the Clinical Response Score subset at Weeks 10 and 16
- The change from baseline in serum CRP levels at Weeks 10 and 16
- The change from baseline in fecal calprotectin levels at Weeks 16
- The change from baseline in the IBDQ domain and total scores at Weeks 10 and 16

10 Safety

10.1 General Considerations

Safety parameters will be evaluated for the safety analysis set by treatment group.

10.2 Adverse Events

Adverse events (AEs) will be classified according to the MedDRA version 17.1 or later.

Written narratives will be issued for all serious AEs (including deaths) and AEs leading to discontinuation.

A 'pre-treatment' AE will be defined as an AE that occurs between screening and the first dose of the IMP. A 'treatment-emergent AE (TEAE)' will be an AE which occurs in the time interval from initial dosing (IMP intake) to the end of treatment visit. If an AE on Day 1 occurs before IMP intake, it will be recorded as a pre-treatment AE. An AE that occurs after the first dose of the open-label period will be considered a TEAE for the open-label period.

If causality is missing, the AE will be regarded as being reasonably possibly related to IMP. Related AEs (judged as being reasonably possibly related to IMP) will be termed adverse drug reactions (ADR).

10.2.1 Overview of Treatment-Emergent Adverse Events

An AE overview summary table will be prepared including the number of subjects reporting an AE, the percentage of subjects (%) with an AE, and the number of events (E) reported, for the following categories:

- Any TEAEs
- Deaths
- Serious adverse events
- Adverse events leading to discontinuation
- Severe TEAEs
- Adverse drug reactions

A similar summary table will be provided for the AEs occurring during the open-label period for subjects who receive the open-label treatment.

